Irradiation effect is a proprioceptive neuromuscular facilitation technique that causes an overflow of neuronal energy from distal to proximal muscles to increase muscle activity of a targeted muscle^{13,14}. This technique can be used to selectively recruit weaker motor units through the application of resistance or stimulation¹³⁻¹⁵. By inducing a stronger contractile force of the quadriceps, our hope is to return quadriceps function to normal quicker with less atrophy and greater strength^{3,6,12}.

We hypothesize that ankle positioning in maximal dorsiflexion (DF) changes the quantity of contraction as a percent of the reference voluntary contraction when performing a supine straight leg raise compared with having the foot in neutral (0°), relaxed, and plantarflexed (PF) positions. This may help provide insight into proper instruction and cuing for patients to return quadriceps neuromuscular control sooner and thus limiting quadriceps atrophy.

2 Objectives

Aim 1: Determine the effects of ankle positioning on quadriceps neuromuscular activation during supine straight leg raises.

Aim 2: Determine if there is a difference between ankle positioning on quadriceps neuromuscular activation during straight leg raises in supine in healthy versus post-operative participants.

3 Participant Eligibility

All Participants

Inclusion Criteria:

- Males and females ages 18-55

Exclusion Criteria:

- History of diagnosed cancer, neurological disorder, peripheral nerve injury affecting the lower limb or injury to the lower spine with radicular symptoms, which may affect quadriceps activation
- History of musculoskeletal injury to the quadriceps that may affect ability to maintain muscle contractions without excessive fatigue or discomfort

Healthy Controls

Exclusion Criteria:

- Injury to the knee or the quadriceps muscle group within the past 12 months to the tested side
- History of lower extremity orthopedic surgery in the past 12 months to the tested side

Participants with Arthroscopic Knee Surgery

Inclusion Criteria:

- Arthroscopic knee surgery including a meniscectomy, chondroplasty, debridement, loose body removal, and plica excision within the past 28 days
- Scheduled for physical therapy at Andrews Institute Rehabilitation

Exclusion Criteria:

- Multiple ligament reconstruction
- Total joint arthroplasty
- Major surgical complication (infection, deep vein thrombosis, surgical revision, neural impairment/pathology)

4 Participant Enrollment

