We intend to enroll 100 volunteers. 50 participants with knee arthroscopy to be tested within the first 28 days after surgery and 50 healthy control participants will be recruited for this study by word of mouth and participants will be screened for inclusion and exclusion criteria. Healthy control participants will be matched by age and leg tested (dominant or non-dominant) with participants in the knee arthroscopy group. Dominant leg will be identified as the leg that the participant uses to kick a soccer ball. Potential participants will have the study described to them including potential risks and will be given the opportunity to read and sign an approved informed consent form. This process will take place prior to any study related activities. If the participant meets inclusion and exclusion criteria, the participant will be scheduled for a testing appointment at the Andrews Research & Education Foundation.

5 Study Design and Procedures

Participants will be screened for all inclusion and exclusion criteria during subject recruitment and will be asked to refrain from heavy lifting, exercise, and any activity that may cause fatigue of the leg muscles 24 hours prior to the testing session. The participants who have undergone knee arthroscopy will be tested on a day they have not done physical activity. The participant's age, date of birth, height, weight, and surgical history (if applicable) will be collected on the Knee History Form (attached), which has been adapted from the 2000 International Knee Documentation Committee Knee History Form, and participants will complete the visual analog scale for pain (VAS).

Participants will have surface electromyography electrodes placed on the skin overlying the vastus medialis oblique (VMO), rectus femoris (RF), vastus lateralis (VL), and tibialis anterior (TA). Electrode locations will be identified through palpation of the muscle belly and electrodes will be placed according to SENIAM recommendations. The identified locations for electrode placement will be shaved, abraded, and cleaned using standard medical alcohol swabs. Subsequent to surface preparation, adhesive Noraxon Single Electrodes, 4cm Ag/AgCl diameter disk shaped, surface electrodes (Noraxon USA, INC, Scottsdale, Arizona) will be attached over the muscle bellies and positioned parallel to muscle fibers using previously published standardized methods.¹⁶ Electrodes will not be replaced or moved throughout the entire data

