Participants will place the foot in the desire position prior to the quad set and any motion of the leg and will maintain the foot position throughout the motion of the task. The participant will then perform a quad set holding for 1 second, then raise the leg taking approximately 1 second to raise the leg to the height of the contralateral limb with the knee flexed to 90° (based off goniometric measurements), hold for 1 second at the top and lower during the SLR taking approximately 1 second, then continue to hold the quad set for 1 second with the foot in the specified position while the leg is on the table, then relaxing. During the quadriceps set the participant will actively contract their quadriceps for a maximum total of 5 seconds performing 5 repetitions in each foot positioning and the muscle activation will be recorded. The knee will be extended active maximally as is customary with the performance of a quadriceps set and straight leg raise with the participant in the supine position, and remain extended throughout the task. Participants will be asked to maximally contract their quadriceps for the duration of the task as well. There will be a minimum of 1 second duration during both the concentric and eccentric

phases of the movement. Participants will have a minimum of 60 seconds of rest between each repetition.

Before starting each straight leg raise, a rest period of muscle activity will be recorded with the participants ankle in the respective testing position (active maximal DF, PF, and a relaxed foot position). This will allow for the option for the EMG signal to be rectified and adjusted for baseline noise by subtracting the mean of the rectified signal during the quiet period (before the start of each exercise) from the rectified signal.

Analysis will be performed with the first repetition and the last repetition being omitted and the average of the remaining 3 repetitions will be done for each testing position for both controls and intervention groups.

A video camera will be used to record the performance of each exercise. EMG and video acquisition will be synchronized. Each repetition will be sub-divided in 2 phases: concentric phase defined as when the participant works against gravity to actively lift their leg of eccentric phase defined as when the participant works against gravity to slow down the return to the starting point of the concentric phase.

6 Expected Risks and Benefits

Risks and Discomforts:

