Data will be analyzed using custom-built MATLAB Software. Rectified EMG will be smoothed and filtered according to standard procedures for human surface EMG. Root mean square values will be calculated and normalized to the reference voluntary contraction. Root mean square values will be calculated for each repetition of the SLR and for each of the three phases (isometric, concentric, and eccentric) and across the whole trial. Processed data will be exported to Microsoft Excel and SPSS.

9 Statistical Considerations

Statistical analysis will be performed in excel and SAS Studio (Version 3.8 on SAS 9.4, SAS Institute Inc., Cary, NC). A 2 (group) x 4 (position) x 3 (phase) MANOVA will be performed for each muscle and appropriate post-hoc tests will be used to ascertain differences among variables. The alpha level will be set *a priori* at $p < .05$.

10 Quality Control and Assurance

All protocols will be monitored and analyzed data will be checked for accuracy by the principal investigator and/or a designated research team member. All medical data will be kept in compliance with HIPAA guidelines.

11 Regulatory Requirements

Informed Consent:

The informed consent process will be performed by one of the study investigators or staff. All participants will have the study described to them and will be given as much time as they would like to read an approved, stamped version of the informed consent document. After signing the informed consent document, they will be given a copy for their records. This process will take place at the AREF.

Participant Confidentiality:

Participant confidentiality information is listed above in #7 (Data Management Procedures). All medical data will be recorded and stored in compliance with HIPAA guidelines.

Quadriceps Activation Comparative Analysis Based on Positioning of the Ankle during Supine Straight

Leg Raise.

[name] DPT, SCS, CSCS

Page 7 of 9

12 References

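### The optional EMG noise correction takes its baseline with active maximal dorsiflexion already held, so if used it can remove pre-exercise overflow from dorsiflexion trials as noise and shift the dorsiflexion-minus-relaxed contrast downward

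*Protocol*

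**What the plan says.** Section 5 (Study Design and Procedures) sets the order of events: "Participants will place the foot in the desire position prior to the quad set and any motion of the leg". Before each straight leg raise "a rest period of muscle activity will be recorded with the participants ankle in the respective testing position (active maximal DF", plantarflexion or relaxed). The purpose follows: "This will allow for the option for the EMG signal to be rectified and adjusted for baseline noise". The method is "subtracting the mean of the rectified signal during the quiet period (before the start of each exercise) from the rectified signal".

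The recorded muscles, also in Section 5, are "vastus medialis oblique (VMO), rectus femoris (RF), vastus lateralis (VL), and tibialis anterior (TA").

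Section 1 explains irradiation as a technique that "causes an overflow of neuronal energy from distal to proximal muscles to increase muscle activity of a targeted muscle", and it hypothesises that "ankle positioning in maximal dorsiflexion (DF) changes the quantity of contraction as a percent of the reference voluntary contraction" compared with neutral, relaxed and plantarflexed positions.

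Section 8 (Data Analysis) gives the processing chain: "Rectified EMG will be smoothed and filtered according to standard procedures for human surface EMG", then root mean square (RMS) values, then normalisation to the reference voluntary contraction. The baseline subtraction does not appear there.

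**The concern.** A noise baseline should contain only what has nothing to do with the condition under test. Here it is taken separately in each ankle position, after the position has been assumed, so in DF trials it is taken during a maximal contraction of the distal muscle. The amount subtracted can therefore vary with the factor whose effect Aim 1 is meant to estimate. It may also contain the overflow that Section 1 gives as the reason to expect an effect.

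If that happens, a positive DF effect is understated and a negative one is exaggerated. A true effect of zero would appear as a decrease. The hypothesis says only that DF changes the quantity of contraction, so an artefactual decrease could be read as a result.

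For tibialis anterior no assumption about overflow is needed. Holding active DF is a deliberate contraction of that muscle, and Section 9 runs the analysis for each muscle.

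**Working it through.** The protocol states no figure on this point, so there is none to reproduce. The check is algebra on its own correction, then an illustration on assumed values.

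**Inputs from the protocol.** Baseline recorded with the test position held, and mean rectified signal subtracted (Section 5); RMS normalised to one reference contraction (Sections 5 and 8).

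**Assumed inputs.** Amplitudes are fractions of the relaxed task amplitude. Let *n* be the noise floor, *r* the quadriceps activity evoked by holding DF before the exercise, and *D* and *R* the DF and relaxed task levels. Overflow and noise are independent signals and add in power, so the baseline level is *n* in relaxed trials and *h* = √(*n*² + *r*²) in DF trials.

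**Direction (mean rectified level).**
- Common relaxed baseline: (*D* − *n*) − (*R* − *n*) = *D* − *R*.
- Position-specific baseline: (*D* − *h*) − (*R* − *n*) = (*D* − *R*) − (*h* − *n*).

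The shift is −(*h* − *n*). It is zero if *r* = 0 and negative for any *r* above 0. It equals −*r* only when there is no noise floor; otherwise it is smaller in size.

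**Normalisation does not remove it.** One reference scales all positions alike. If the reference trials were corrected with the same DF-held baseline, the divisor would shrink too, but the shift stays downward as long as the contrast is smaller than the corrected reference level. Example (assumed): reference 100, *D* = 100, *R* = 90, noise 2, and 5 further units in the DF baseline. The contrast is 5/93 = 5.4%, against 10/98 = 10.2% with a common baseline.

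**Illustration, smoothed signal.** Section 8 smooths the rectified EMG before RMS. Take a true DF-minus-relaxed difference of +10%. With *n* = *r* = 5%: *h* = √(25 + 25) = 7.07%, the shift is −2.07 points, and the estimate is 7.9%. Simulated band-limited Gaussian EMG with a 100 ms smoothing window (the window is an assumption) gives, in % of the uncorrected relaxed level:

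| Noise floor | *r* = 2% | *r* = 5% | *r* = 10% | *r* = 20% |
|---|---|---|---|---|
| none | 8.0 | 5.0 | 0.1 | −9.9 |
| 1% | 8.8 | 5.9 | 1.0 | −8.9 |
| 5% | 9.6 | 7.9 | 3.9 | −5.5 |

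The formula 10 − (*h* − *n*) agrees with every cell to within about 0.15 point.

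**Illustration, unsmoothed signal.** For Gaussian EMG of amplitude *s* and subtracted mean *b*, RMS(|x| − *b*) = √(*s*² − 2*kbs* + *b*²), with *k* = √(2/π) = 0.798 and *b* = *k* × baseline level. With *n* = *r* = 5%:
- DF: *s* = √(1.21 + 0.0025) = 1.1011 and *b* = 0.0564, so RMS = 1.0567.
- Relaxed: *s* = √(1 + 0.0025) = 1.0012 and *b* = 0.0399, so RMS = 0.9697.
- The difference is 0.0870, or 8.7%.

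For *r* = 2/5/10/20% and 5% noise, the estimates are 9.7/8.7/6.2/+0.5%. The shifts are smaller than in the smoothed case.

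**The case against.** The strongest reply is that the analysis as written contains no subtraction. Section 5 only keeps the option open, and Section 8 goes from rectification to smoothing, RMS and normalisation without it. Whether to use an optional processing step may properly be settled in a statistical analysis plan. This stands, and leaving the choice open is not the fault raised here. The fault is that the option, as Section 5 defines it, uses a baseline unsuited to its stated purpose.

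Second, no section says that holding DF activates a resting quadriceps. Section 1 describes overflow under applied resistance or stimulation and hypothesises an effect during the leg raise. Overflow that arises only during the task is kept. This also stands: *r* may be zero. But with overflow as the study's own rationale, zero is not a safe default.

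Third, a position-matched baseline could be intended to isolate activity added by the task, and it follows noise from repetition to repetition. The first purpose is legitimate, but Section 5 gives the purpose as removing noise, and Section 1 hypothesises the quantity of contraction itself. The loss of drift tracking is real, and its size is given with the fix.

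A reader might infer more than this: that the DF result will be biased, that the bias equals the overflow, or that the comparisons with plantarflexion and between groups are biased too. The documents support none of these. The step may never be applied. The shift equals *r* only without a noise floor. Plantarflexion trials also have a baseline with the position held, so the direction for DF versus plantarflexion is undetermined. Nothing shows that resting overflow differs between surgical and healthy participants, so no effect on Aim 2 follows.

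**Conclusion.** The concern holds in conditional form. If the optional subtraction is used and holding DF evokes any quadriceps activity beforehand, the DF-minus-relaxed contrast is shifted downward relative to a common baseline. For the quadriceps the direction is established and the size is not.

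On the assumed values, the loss from a true +10% runs from 0.3 point (*r* = 2%, 5% noise, unsmoothed) to 19.9 points (*r* = 20%, no noise, smoothed). A change of sign needs resting overflow to be large relative to the true effect. In the smoothed illustration, it occurs between *r* = 10% and 20% at every noise level shown.

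For tibialis anterior, the DF baseline contains deliberate contraction whatever *r* is, so the label of noise correction is wrong there. Both aims concern the quadriceps, which limits the weight of that part.

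Priority is minor to moderate, because the effect depends on an optional step and an unknown *r*.

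**What to change.** In Section 5, choose one of two statements.

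- State that no baseline subtraction is done. This agrees with Section 8 as it stands.
- Or state: *If EMG is adjusted for baseline noise, one common value per muscle and limb, the mean rectified EMG of all relaxed-foot rest recordings of the session, will be subtracted identically in all foot positions and in the reference trials. Whether the adjustment is applied will be fixed before analysis.*

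In either case keep the rest recordings made in DF and plantarflexion as a descriptive measure of overflow. They would also show how large *r* is.

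The cost is a sentence or two of text and, for the second choice, a small code change, since the relaxed-foot recordings are already planned. The downside is that noise drift between repetitions is no longer tracked. If the noise floor rose from 1% to 5% or 10% of the relaxed amplitude, with all of the drift falling on DF trials (assumed), the contrast would move by √(1 + 0.05²) − √(1 + 0.01²) = 0.12 or √(1 + 0.10²) − √(1 + 0.01²) = 0.49 percentage points.
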